4.2 Study Timeline

Aim for REC Approval	Jan 2025
Study site R&D approval and site setup	Jan 2025
Recruitment (Visit 1) window	Jan 2025 – Jul 2025
Sample processing starts	Oct 2024
Follow-up visit 2 window	Apr 2025 – Jan 2026
Visit 1 samples bacterial genomic sequencing & analysis	Jul 2025 – Sep 2025
Follow-up Visit 3 window	Oct 2025 – Jul 2026
Last participant last study visit	Jul 2026
Sample processing end	Jul 2026
Visits 2 & 3 sample sequencing & complete analysis	Jul 2026 – Apr 2027

See *Section 5 Study Schedule* for more information on study visits.

End of study: The end of the study is defined as once all study visits for every participant have been completed, all study samples processed and undergone bacterial genomic sequencing, and data has been checked and locked. Data analysis will be ongoing at the end of the study.

4.3 Sample Size

Target sample size 108. This assumes an overall prevalence of AMR in the gut of 32.5%.^[19] Under this assumption, the proposed sample size for this study will allow the prevalence of SPEAR, EDGE (Sponsor) number 174194, IRAS 330315, Protocol, 1.1, 16/DEC/2024

AMR genes of interest across all study participants to be estimated with 95% confidence intervals (CI) +/- 8.85%. The prevalence within the groups of 36 will be possible to estimate with 95%CI +/- 15.5%. This precision will be sufficient to inform the feasibility of larger AMR surveillance research and programmes in the same patient population. In each group of 36 participants, it is expected to observe 11 cases of AMR, with 99% probability of observing at least six cases in each subgroup. This will allow piloting all aspects of specimen processing, genome sequencing, data processing and transfer workflows.

4.4 Visit Activities and Samples

There are 3 planned visits for this study (see *Section 5 Study Schedule*). All data and samples will be pseudonymised. A unique identifier (participant ID) will be assigned to each participant enrolled in the study. The participant ID will be used for sample labelling and questionnaire completion. All study activities and procedures will be undertaken after eligibility has been confirmed and informed consent has been given (see *Sections 6 Eligibility Criteria* and *8 Consent* for more details).

At each of the study visits the following three steps will be undertaken:

Step 1: Questionnaire

Participants will self-complete an electronic questionnaire. This will be pseudonymised using the participant ID number, and obtain information on demographics, medical history, sexual activity, STI prophylaxis use, any other antibiotic use, and travel. This will be completed on a tablet or computer in a private clinic room with a member of the research team on hand in case of difficulty or queries. Where possible, the questionnaire incorporates validated questions from other research surveys. It will take approximately 15 minutes to complete.

Step 2: Oropharyngeal Swab

An oropharyngeal swab will be collected from participants by the member of the research team conducting the study visit. Prior to collecting each sample, the researcher will ask the participant for consent to proceed. All samples will be taken in a private clinic room. The swabs will be labelled with the date of collection, the participant ID, and a sample ID number.

Step 3: Stool Sample

Participants will be provided with a stool sample collection kit. For Visit 1, the kit will be provided during the study visit or posted to the participant prior to the visit if they have completed e-consent (see *Section 8 Consent*). Kits will include instructions on how to collect a stool sample and gloves for the collection. The researcher will explain the process of stool sample collection to the participant at the study visit or by telephone if collecting prior to the visit.

Participants will be offered a range of options for collecting stool samples:

- **In clinic at study visit:** participants providing stool samples during the study visit will be directed to a toilet to collect their own sample.
- **At home after study visit:** participants will be able to provide a stool sample collected at home within 7 days of the study visit and return the sample to the study site within 48 hours of collection.

- **At home before study visit:**
 - **Visit 1:** participants completing e-consent and opting to be posted a stool sample collection kit will collect the sample at home less than 48 hours before the study visit and to bring it with them.
 - **Visits 2 and 3:** At Visit 1, participants will be given kits for follow-up visits to take home and return when they attend for Visits 2 and 3. Participants will be asked to collect the sample at home less than 48 hours before the visit.

Stool samples will be labelled with the date of collection, the participant ID, and a sample ID number.

Sample Storage and Transport

[figure not shown]
Samples will be labelled with the date of collection, unique participant ID, and a sample ID number. Samples will be stored at the study site at -80C for a maximum of 28 days, before being couriered in an appropriate container for microbiology samples to the University of Oxford laboratory (Department of Biology, University of Oxford, [name]) for processing and storage until the end of the study (see **Figure 1** and *Section 13 Material/Sample Storage and Storage*). No study samples will be stored beyond the end of the expected study completion of April 2027.

Sample Processing and Sequencing

Sample specific microbial DNA extraction kits will be used. Extracted bacterial DNA will be stored at the Department of Biology, University of Oxford at -80C prior to metagenomic sequencing. Library preparation and metagenomic sequencing will be undertaken at UCL Genomics ([name]).

Participants will remain in the study for a maximum of 13 months (360 +/- 30 days) (see *Section 5 Study Schedule*)

Figure 1: Sample workflow for Visits 1, 2, and 3.

5 STUDY SCHEDULE

All study visit activities will be conducted by a member of the clinical research team (research doctor, research nurse, or research assistant). For information on identification of potential participants and informed consent please see sections 7 *Recruitment* and 8 *Consent*. Participants receive a £30 voucher for each study visit. This will be given to participants at the end of each study visit. Participants will be able to withdraw from the study at any time. All data and samples collected prior to this will be retained by the research team.

Visit	Schedule (days)	Activities	Length (minutes)
1	0	Informed consent; questionnaire; oropharyngeal swab; stool sample	60
2	180 +/- 30	Questionnaire; oropharyngeal swab; stool sample	30-60
3	360 +/- 30	Questionnaire; oropharyngeal swab; stool sample	30-60

6 ELIGIBILITY CRITERIA

6.1 Inclusion Criteria

- Aged \geq 18 years.
- Identifies as a man (cis or trans).
- Has sex with men.
- Able to provide informed consent.

6.2 Exclusion Criteria

- Use of an antibiotic other than doxycycline in the 3 months prior to enrolment
- Currently being treated for an STI with doxycycline
- Use of doxycycline within the prior 3 months for an indication other than STI treatment or STI prevention.

7 RECRUITMENT

Participant identification and recruitment will be through two distinct methods: clinic-based and community-based. The recruitment strategy has been co-developed with the SPEAR study community advisory group (see *Section 10 PPI*). The study includes online community-based recruitment through targeted adverts on social media and MSM-focused geospatial networking ('dating') apps to ensure the recruitment target for MSM using STI prophylaxis (group A) is met and allow recruitment of MSM not regularly attending in-person SHS or living outside London. Enrolment will be monitored in real-time to ensure targets for each antibiotic exposure group and MSM living with HIV are achieved.

7.1 Clinic-based: Patients attending CNWL SHS

Clinician referral

Clinicians seeing potentially eligible patients will refer them to the research team. The patient will be given the leaflet and PIS to read. If they wish to proceed and are eligible, they will be asked to provide informed consent (see *Section 8 Consent*) and booked for Visit 1 (see *Section 5 Study Schedule*).

Direct approach by the research team

Clinic appointment lists will be screened in advance by a member of the research team for potentially eligible participants. Members of the research team are also members of the clinical team involved in routine sexual health and HIV care alongside research. Patients will be contacted in advance of their appointment or approached in the waiting room. They will be given a copy of the PIS to read. If they wish to proceed and are eligible, they will be asked to provide informed consent (see *Section 8 Consent*) and booked for Visit 1 (see *Section 5 Study Schedule*).

Participant self-referral

Posters and leaflets describing the study will be available in clinical areas. These will include details of the study specific UCL webpage and contact details for the research team. Patients will be able to directly contact the research team by email. They will be sent the PIS to read. If they wish to proceed and are eligible, they will be asked to provide informed consent (see *Section 8 Consent*) and booked for Visit 1 (see *Section 5 Study Schedule*).

These recruitment strategies are used successfully for other studies within CNWL. Participation in the study does not impact the routine NHS sexual health or HIV care being provided to the participant by CNWL. Study visits and study sample collection are conducted independently of routine NHS care provided. The poster/leaflet have been co-designed by the community advisory group (see *Section 10 PPI*).

A log will be kept of potential participants approached in clinic but who decline to participate, alongside a reason for declining if given.

7.2 Community-based online

Social Media

Social media posts promoting the study will be shared on social media. This will include approved images/graphics and recruitment video. A study specific X™ account (formerly Twitter™) will be created to promote the study. Posts will also be shared on existing social media accounts (e.g. X™, Instagram™) associated with the UCL research team and CNWL. The research team have established links with professional organisations (e.g. BASHH) and is collaborating with the LGBTQ+ health focused community group The Love Tank who will promote the study.

MSM-focused geospatial networking ('dating') apps

Paid adverts will be placed on MSM-focused dating apps (e.g. Grindr, Scruff). This recruitment strategy is used successfully for cross-sectional surveys of MSM conducted by UCL.

Online posts/adverts will include a brief overview of the study, information on reimbursement for participation, and details of how to contact the research team. Online posts/adverts have been co-designed by the community advisory group (see Section 10 PPI). Individuals who contact the research team will be sent the PIS and then receive a phone call to discuss the study further and assess eligibility. If they wish to proceed and are eligible, they will be asked to provide informed consent (see *Section 8 Consent*) and booked in for Visit 1 (see Section 5 *Study Schedule*).

8 CONSENT

Informed consent will be gained from participants before any study activities are undertaken. Participants will be given and/or emailed the PIS to read prior to being asked to give informed consent. Participants will have three options for providing informed consent using the latest approved informed consent form (ICF):

1. E-consent prior to the first study visit.
2. E-consent at the start of the first study visit.
3. Written consent on paper ICF at the start of the first study visit.

E-consent will be provided using an online REDCap form. Completed e-consent forms will be stored in a study specific REDCap database within the UCL Data Safe Haven (see *Section 12 Data Handling and Management*) 12.[28] Participants opting for e-consent prior to the first study visit will receive a telephone call from a member of the research team (research doctor, research nurse, research assistant) to explain the study, confirm eligibility, and answer any questions. They will then be emailed a link to the e-consent form to complete and sign. The e-consent form will be signed by the member of the research team taking consent.

Participants opting to provide informed consent at the start of the first study visit will be offered to complete an e-consent or a written consent form. During the informed consent process, the study will be explained, participants will be given time to read the PIS again, and all questions will be answered. Participants opting for e-consent will complete the form online. The e-consent form will be signed by the member of the research team taking consent. Participants opting for written paper consent will sign two paper copies of the ICF. The person taking consent (research doctor, research nurse, research assistant) will also sign both ICFs. One signed ICF copy will be given to the participant and the second copy will be retained and stored securely at the study site (CNWL). A scanned copy of the written or e-consent form will be uploaded to the participant's CNWL-held medical records.

It will be clearly stated that the participant is free to withdraw from the study at any time for any reason without prejudice to current or future care, without affecting their legal rights, and with no obligation to give the reason for withdrawal. Participants will be informed that if they withdraw from the study, any study samples and data already collected will be retained and used in the final analysis. Participants will be asked for specific consent to review their study site medical records.

9 DATA ANALYSIS

9.1 Statistical Analysis

The planned statistical analysis is summarised here. The statistical analysis will be fully outlined in a statistical analysis plan (SAP). The SAP will be written by [name] (Chief Investigator) and [name] (Co-Investigator & Statistician). The SAP will be finalised before any analysis takes place. An analysis of baseline samples will be undertaken once all participants have completed Visit 1.

Sample characteristics, STI prophylaxis use, and questionnaire responses will be described using absolute numbers and proportions. A pooled prevalence estimate with 95% CI for AMR genes/gene mutations of interest will be produced. Chi-square tests will be used to evaluate evidence of differences in prevalence between subgroups, although findings will be presented with caution given the relatively small sample size. The association between detection of AMR genes/gene mutations of interest with demographic and sexual history variables will be described and investigated in exploratory univariable analyses.

Descriptive analyses of AMR detection over time within each group will be conducted. If adequate variation within individuals over time, then generalised estimating equations logistic regression will explore trends over time and consistency of AMR detection within each group.

Statistical analyses will be undertaken on the statistical programmes STATA and R.

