behaviour and antibiotic exposure (given differences in STI risk, testing, and treatment) are important potential confounders when studying microbiomes in MSM and people living with HIV.[18] It has also been suggested that both macrolides and tetracyclines have greater impacts on gastrointestinal microbiota compared to other antibiotics.[19] Moreover, alterations in gastrointestinal microbiome have been associated with metabolic, mental health and autoimmune diseases.[23,24] An oropharyngeal microbiome study noted that prevalence of select AMR genes ('resistome') was lower in the general population compared to MSM (ratio 0.41(0.26-0.65)), but found no difference when comparing MSM with and without recent antibiotic exposure.[25] This small cross-sectional study did not assess antibiotic STI prophylaxis and was limited by the lack of data on sexual behaviour including oral sex and ano-oral sexual contact.[25] Microbiome disturbances are multifactorial and differences in the gastrointestinal and oropharyngeal microbiota require careful interpretation as findings may be confounded by sexual behaviour and living with HIV.[22,27] Despite this, a systematic review of human gut resistome studies included no discussion on the potential impact of sexual behaviour or HIV. [26]

While the evidence of STI prophylaxis efficacy in MSM is compelling, given the lack of data on AMR, global differences in baseline AMR, and the potential addition of long-term antibiotic prophylaxis as a recommended STI prevention strategy in MSM, further research is required in the UK on the risks associated with STI prophylaxis and methods for monitoring and mitigation, such as enhanced surveillance. This research will provide data to fill important evidence gaps and develop the methodologies for further AMR research and optimised surveillance.

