3.2 Secondary Objectives

- A) To assess feasibility and acceptability of recruiting STI prophylaxis users via sexual health clinics versus online and obtaining appropriate samples.
- B) To evaluate the use of shotgun metagenomic sequencing to identify AMR genes or gene mutations conferring resistance to tetracycline and other relevant antibiotic classes.
- C) To evaluate the use of shotgun metagenomic sequencing to identify bacteria present in the gastrointestinal tract and oropharynx of MSM.
- D) To estimate the prevalence of AMR genes/gene mutations of interest and describe changes over time in the gastrointestinal tract and oropharynx of MSM using and not using STI prophylaxis.
- E) To characterise the gastrointestinal and oropharyngeal microbiomes and describe changes over time in MSM using and not using STI prophylaxis.
- F) To develop the methodology for future AMR research and surveillance in MSM and other relevant population groups.

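### Section 9.1 tests prevalence differences between non-randomised exposure groups with a crude chi-square and cautions only about sample size, although Section 2 names confounders

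*Protocol*

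**What the plan says.** Section 9.1 is a summary, with full detail left to a SAP. It names three analyses of AMR gene prevalence:

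- An overall estimate: "A pooled prevalence estimate with 95% CI for AMR genes/gene mutations of interest will be produced".
- A between-group comparison: "Chi-square tests will be used to evaluate evidence of differences in prevalence between subgroups", with the qualification that "findings will be presented with caution given the relatively small sample size".
- Associations with demographic and sexual history variables, which "will be described and investigated in exploratory univariable analyses".

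It also plans within-group descriptions over time and, if the data vary enough within person, a GEE model within each group. Neither is an adjusted comparison between groups.

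Objective D in Section 3.2 concerns prevalence and change in the gut and "oropharynx of MSM using and not using STI prophylaxis". Section 4.3 gives by-group precision: "The prevalence within the groups of 36 will be possible to estimate with 95%CI +/- 15.5" per cent. Section 9.2 plans to compare resistome profiles between the baseline groups and by doxycycline prophylaxis use.

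On confounding, Section 2 says that sexual behaviour and "antibiotic exposure (given differences in STI risk, testing, and treatment) are important potential confounders when studying microbiomes in MSM", and that "findings may be confounded by sexual behaviour and living with HIV". Both remarks are about microbiomes. In its AMR part, Section 2 cites *mphA* prevalence of 32.5% overall and 41.3% in men with a bacterial STI diagnosed in the previous 12 months.

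Section 4.1 sets 36 men per group by recent antibiotic exposure and puts anyone who qualifies for both A and B into A.

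**The concern.** Men choose prophylaxis, and men receive STI treatment, for reasons tied to sexual behaviour and STI history. Those factors may also be related to carriage of resistance genes. A crude A–C or A–B difference could then be read as reflecting prophylaxis when part of it reflects behaviour or past STIs.

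Small sample size is a different problem. It widens the interval around the crude difference but says nothing about where that interval is centred, and a larger study would remove the stated caution without removing the bias. The univariable analyses can show that a sexual history variable is associated with AMR detection. They cannot show what it does to the A/B/C contrast.

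The allocation rule adds a second mixture. Group A can contain men with both prophylaxis and a recent doxycycline treatment course, so an A contrast is not a contrast of prophylaxis alone.

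At stake is how a secondary result is read in a study whose aim includes informing decisions on STI prophylaxis. The primary feasibility objective is not affected.

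**Working it through.** **1. The protocol's own precision.** Inputs from Section 4.3: prevalence p = 0.325, N = 108, n = 36 per group. The Wald half-width is 1.96 × √(p(1−p)/n), with p(1−p) = 0.219375.

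- N = 108: 1.96 × √(0.219375/108) = 8.83 points (protocol 8.85).
- n = 36: 1.96 × √(0.219375/36) = 15.30 points (protocol 15.5).
- P(at least 6 cases of 36) = 0.990 (protocol 99%).

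The stated figures reproduce closely enough, so there is no arithmetic error.

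**2. Random error in a two-group contrast.**

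- Half-width of a difference, 36 v 36: 1.96 × √(0.219375 × 2/36) = 21.6 points.
- Power at 32.5% v 65% (mean 48.75%), two-sided 5%: [0.325 × √36 − 1.96 × √(2 × 0.4875 × 0.5125)] / √(0.219375 + 0.2275) = (1.950 − 1.386)/0.668 = 0.84, so 80%. A true gap of about 32.5 points is needed.

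The sample-size caution is therefore justified as far as it goes.

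**3. What the design already controls.**

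- HIV: 12 to 13 ring-fenced places per 36 is 33.3% to 36.1%, a floor that differs between groups by at most 2.8 points.
- Other antibiotics: Section 6.2 excludes non-doxycycline use in the previous 3 months.
- Sexual behaviour and STI history: not balanced by any rule, and recent STI treatment is what defines group B.

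**4. Possible confounding by one binary behaviour measure.** Bias = imbalance between groups × prevalence gap. The protocol gives neither input, so both are assumptions.

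| Imbalance | Gap 5 points | Gap 20 points |
|---|---|---|
| 0 | 0 | 0 |
| 20 points | 1.0 | 4.0 |
| 40 points | 2.0 | 8.0 |

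The cited *mphA* figures differ by 41.3 − 32.5 = 8.8 points. That compares men with a recent STI against all men, and it concerns azithromycin resistance. It supports an association with STI history but does not supply the gap for tetracycline genes.

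**5. Precision cost of stratifying A v C on that measure.** With Mantel-Haenszel weights n₁n₀/(n₁+n₀) and p = 0.325 throughout, the half-width is 1.96 × √(0.219375/Σw).

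- 60% v 40%: w = 21.6 × 14.4/36 = 8.64 per stratum, Σw = 17.28, half-width 22.1.
- 70% v 30%: w = 25.2 × 10.8/36 = 7.56 per stratum, Σw = 15.12, half-width 23.6.

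**6. Precision cost of leaving out dual-exposed men.** Their number is not given; 4 to 11 of 36 is assumed.

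- Group A prevalence: n = 32 gives 16.2 points, n = 25 gives 18.4 (from 15.3).
- A–C difference: 32 v 36 gives 22.3 points, 25 v 36 gives 23.9 (from 21.6).

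**7. Room for covariates.** Expected positives are 108 × 0.325 = 35.1. Two group terms, HIV status and one behaviour measure make four terms: 35.1/4 = 8.8 per term. There is no room for more.

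**8. What the pooled figure describes.** Group A is 36/108 = 33.3% of the sample by quota. Section 2 puts prophylaxis use at 3% to 10% among MSM on HIV-PrEP or living with HIV. The pooled estimate averages over the quota mix.

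**The case against.** The strongest reply is that Section 9.1 only summarises, and that adjustment, by-group tables and sensitivity sets normally belong in the SAP, which is to be final before analysis. That stands as far as absence goes: the SAP may well contain all of these. It does not cover what 9.1 states, which is a crude test for non-randomised groups with a caution that gives one reason and leaves out the one Section 2 raises.

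A reader might infer that the protocol plans no by-group estimates and reports only a pooled figure. The documents do not support that. Section 4.3 foresees prevalence within each group of 36 with an interval, a chi-square needs the group prevalences, 9.1 describes AMR detection within groups over time, and 9.2 compares resistome profiles by group and by prophylaxis use. What remains is that the one estimate 9.1 names with an interval is the pooled one.

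Three further points stand as limits:

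- Section 9.1 does not define subgroups. Reading the word as including A, B and C is an inference, supported by Section 4.3, which uses it for the groups of 36. Objective D's split into users and non-users is also not identical to A/B/C.
- Objective D estimates and describes; it makes no causal claim.
- The confounding remarks in Section 2 concern microbiomes. They carry over because the AMR genes are read from the same stool and throat samples, but the protocol does not say so.

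**Conclusion.** The point holds as a minor improvement to the analysis text. Section 9.1 names an unadjusted comparison of self-selected exposure groups, and its caution covers imprecision but not confounding. Group A contrasts can also mix prophylaxis with treatment courses because of the allocation rule.

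A reader might go further and conclude that the crude comparison will be biased by a known or large amount. The documents do not determine the size of any bias. The 1 to 8 points above rests on assumed imbalances and gaps for a single measure, is zero if the groups are balanced, and is well below the 21.6-point half-width. HIV status and other recent antibiotic use are already limited by design. All half-widths assume 32.5% prevalence, which comes from one macrolide-resistance gene and need not apply to the tetracycline genes.

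The comparison is secondary and exploratory in a feasibility study. No stated number is wrong and the primary objective is untouched.

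**What to change.** Amend Section 9.1 and carry the changes into the SAP:

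1. Report the by-group prevalences with 95% intervals that Section 4.3 already foresees (about ±15 points) beside the pooled figure, and label the pooled figure as describing the 36/36/36 quota sample.
2. Beside the crude chi-square, report one sparse exploratory adjusted comparison using a single prespecified sexual-behaviour measure: either Mantel-Haenszel stratified by that measure, or penalised logistic regression with group, that measure and HIV status. State that it does not remove the STI-history differences that define group B.
3. As a sensitivity analysis, repeat the group A contrasts without men who also had recent doxycycline treatment for an STI.
4. Extend the caution, for example: *Group comparisons are descriptive and may be confounded by sexual behaviour and STI history, as well as imprecise.*

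The cost is a few sentences and a little more analysis. No new data are needed: the Section 4.4 questionnaire already covers sexual activity, medical history, prophylaxis and other antibiotic use, and recent doxycycline treatment is established when groups are assigned. Intervals widen somewhat: the A–C half-width goes from 21.6 to about 22 to 24 points under the assumptions above. With about 35 expected positives, no further covariates should be added.
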